Scan Days - Day of T1: T1 will occur as soon as possible after at least 14 days of abstinence. Please note that the exact schedule may need to be modified due to unforeseen events, such as participants arriving late or encountering some form of difficulty and participant schedules. Participants who are caffeinated beverage drinkers will be given a caffeinated beverage (coffee, tea, soda, etc) in order to prevent caffeine withdrawal which may affect the brain reward circuit. (The exact schedule of caffeine, nicotine and food intake may need to be varied to account for changes in the schedule.) All patients with SCZ will be asked to take their usual morning antipsychotic medication at approximately the same time as usual. When participants arrive at the hospital for their scan, they will undergo urine/breathalyzer/pregnancy testing and they will be given breakfast (or similar meal as applicable). Assuming confirmation of continued abstinence (and non-pregnant status), an intravenous line will be inserted with a heparin lock to allow for blood draws (to make the conditions similar to T2, in which participants in Groups 1, 2, and 3, and in Groups 5, 6, and 7 are given an intervention (dronabinol or a cannabis cigarette) and have several tubes of blood drawn.) Lidocaine may be applied to or injected into the skin prior to inserting the needle for patient comfort. At T1, a single specimen of blood will be drawn from all groups to assess participant THC level. Also, if the participant uses nicotine products they will be asked to use these nicotine products at specified times and blood will be drawn to assess the person's nicotine level. All participants will be asked to rate their mood. Participants with CUD will be asked to rate their craving, liking and high. Staff will take vital signs. Participants with SCZ will be rated with brief assessments for psychotic and negative symptoms, as well as EPS. At intervals throughout the day, they will again rate their high, liking, mood and craving and their vital signs will be assessed. The fMRI protocol is described below. After leaving the scanner, they will rate their high, liking, mood and craving, their vital signs will be taken and they will be assessed for reward responsiveness, rated for psychotic and negative symptoms, as well as EPS, and brief

cognitive testing (see below) will be performed. A schedule of events explaining which tasks will occur with the various groups is attached.

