Participants will be instructed to continue to maintain abstinence and will be given an appointment for the next fMRI testing day, as well as for a visit at their local clinic to give a urine drug screen and breathalyzer (if appropriate). To assess for possible adverse events from the procedures, participants in all groups will be contacted the day after discharge from the laboratory.

Note: If participants need an abbreviated schedule for Scan 1 to work around schedule constraints (work, school, childcare), we will accommodate this by eliminating time gaps between the events of the day. The study team may also move the start of the day earlier or later to accommodate participant schedules.

Day of T2 (to occur approximately 7 days after T1):

Groups 1, 2 and 3 (dual diagnosis participants): Prior to receiving the study capsules and study cigarette all participants in these groups will be assessed by a study physician to determine that they are stable and can safely continue with the study visit. Participants in Group 1 will receive 2 (double-blinded) placebo capsules and a 3.6%* cannabis cigarette; participants in Group 2 will receive two 7.5 mg dronabinol capsules and a placebo cigarette; and participants in Group 3 will receive two placebo capsules and a placebo cigarette. Research assessment staff will be blind to group assignment. The pill and cigarette will be dispensed at times to facilitate peak THC levels during the scans. All other procedures outlined for the T1 testing period, above, will apply. When smoking the cannabis or placebo cigarette, participants will be instructed in the use of the "Foltin" method:¹⁵⁵ "light the cigarette" (approximately 30 seconds); "prepare to smoke" (approximately 5 seconds); "inhale" (approximately 5 seconds); "hold smoke in lungs" (approximately 10 seconds); and "exhale". They will smoke 3 puffs in this manner, or until they have consumed 2/3 of the cannabis cigarette.¹⁴ Blood draws will occur for assessment of THC at set intervals. If the participant uses nicotine products blood will also be drawn to assess the person's nicotine level.

* We will obtain our cannabis cigarettes (and placebo cigarettes) from NIDA based on their available stock. We will aim for approximately 3.6% THC cigarettes for the active THC cigarettes.

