Groups 4 and 8 (control participants with SCZ without CUD, and normal controls): These control participants will follow the same protocol as participants in Groups 1, 2 and 3, except that they will not be given capsules or a cannabis cigarette at T2. Although they will have an intravenous line inserted, but only a single blood specimen drawn to confirm abstinence from THC. If the participant uses nicotine products, blood will also be drawn to assess the person's nicotine level. Control participants with SCZ (Group 4) who are regular cigarette smokers

will smoke a cigarette prior to the fMRI protocol as described for Groups 1, 2 and 3. Normal control participants (Group 8) will not be cigarette smokers.

Groups 5, 6 and 7 (control participants with CUD without SCZ): These control participants will follow the same protocol as participants in Groups 1, 2 and 3, including the intervention at T2. Those who regularly use nicotine products will use these nicotine products prior to the fMRI protocol and have blood drawn to assess the person's nicotine level as described for patients in Groups 1, 2 and 3.

At the end of the T2 testing sessions, participants in Groups 1 - 3 and 5 - 7 will be assessed by an MD to ensure that they are able to safely leave the laboratory. Lorazepam and haloperidol will be available in case of untoward reactions to dronabinol or cannabis. All scans occur at a medical center thus treatment will be available as needed based on the presenting medical issue. If participants are deemed unstable clinically, they will be observed further until stable or they will be admitted overnight. To monitor for reactions from the drug or procedures, all groups will be contacted the day following T2 and again approximately one week after T2 for a brief check-in. At the one-week call, Group 1-3 participants will be assessed for cannabis and other substance use (TLFB), psychiatric symptoms (using items from the PANSS Positive Scale) and adverse events. Group 5-7 participants will be assessed for cannabis and other substance use (TLFB), and adverse events. If participants are having clinical difficulties, we will ensure that appropriate treatment is initiated. Participants will be contacted approximately 30 days after the end of the protocol to assess for any changes in adverse events.

We may repeat assessments in cases of unplanned technical difficulties or need to further evaluate or monitor participants and would compensate accordingly.

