Aim 3 a, b (Group X Time effects of dronabinol on "high", liking, craving, mood, negative and positive symptoms, EPS and cognition in SCZ-CUD: These measures (other than cognition) will be taken in patients with SCZ-CUD (G2) prior to the fMRI scan and before dronabinol pill ingestion (Pre) and immediately after the MRI scan is completed (Post). We will conduct additional analyses to test the specific hypotheses that G2 patients will show: (a) improved

mood, reduced negative symptoms and EPS, and no significant change in psychotic symptoms from Pre to Post; and (b) a greater degree of change (from Pre to Post) in these measures than will those in G3, G4, G7, or G8. For cognitive measures, in which we will use assessments at T1 and T2, we will first conduct a Group (G2, G3, G4, G7, G8) X Time (T1, T2) mixed-model repeated measures ANOVA.

c) Justify the sample size, using the concepts of power, type I error, and effect size if applicable. If a formal protocol for the study exists, page references to the protocol are acceptable.

For Aim 1a (i), our pilot fMRI MID data comparing 12 healthy controls and 12 patients with SCZ-CUD yielded a Cohen's d of 1.10 during anticipation of reward for the accumbens ROI. For Aim 1a (ii), our pilot data on group differences in baseline RSC (12 SCZ-CUD; 12 controls), indicated effect sizes ranging from 0.84 to 1.28. For Aim 1a (iii), our pilot data on reward bias revealed a d of 0.77 for the group difference. Based on the above, we expect Aim 1a to be well powered (for 75 patients with SCZ-CUD and 25 normal controls) with effect sizes of $d \geq 0.7$ detectable with adequate power ($\geq 80\%$). For Aim 1b, the fMRI/MID studies of Juckel et al. showed deficient accumbens response during the MID task in patients with

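### Does Aim 3(b) rely on symptom and EPS ratings in G7 and G8 that the scan-day text never describes before the scan?

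*Combined protocol and SAP*

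**What the plan says.** Section 7b, Aim 3 a, b, defines the timing of the ratings for the dronabinol patients: they "will be taken in patients with SCZ-CUD (G2) prior to the fMRI scan and before dronabinol pill ingestion (Pre"), and again straight after the scan (Post). Hypothesis (a) predicts, within G2, better mood, fewer negative symptoms, less EPS and no significant change in psychotic symptoms. Hypothesis (b) predicts "a greater degree of change (from Pre to Post) in these measures than will those in G3, G4, G7, or G8".

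Section 4, Scan Days - Day of T1, allocates the pre-scan ratings. For mood and the cannabis-related scales: "All participants will be asked to rate their mood. Participants with CUD will be asked to rate their craving, liking and high". For symptoms and EPS: "Participants with SCZ will be rated with brief assessments for psychotic and negative symptoms, as well as EPS". The section closes with a pointer: "A schedule of events explaining which tasks will occur with the various groups is attached". The T2 text for Groups 1, 2 and 3 adds: "All other procedures outlined for the T1 testing period, above, will apply".

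At the one-week call (section 4, Day of T2), Groups 1-3 are assessed for "psychiatric symptoms (using items from the PANSS Positive Scale) and adverse events" as well as substance use. For the groups with cannabis use disorder alone, "Group 5-7 participants will be assessed for cannabis and other substance use (TLFB), and adverse events".

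**The concern.** A Pre-to-Post change needs a Pre value. G7 and G8 contain nobody with schizophrenia, so the sentence that hands out the pre-scan symptom and EPS ratings does not name them. Yet hypothesis (b) uses both as comparators for those measures.

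Two other features fit the narrow reading. The one-week call gives PANSS items to Groups 1-3 and none to Groups 5-7. The section 4 overview treats EPS as an effect of antipsychotic drugs, while section 5 excludes psychotropic medication in Groups 5-7 and in Group 8.

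If the narrow reading is right, the plan names a comparison that its described data collection cannot fully supply. A reader may also wonder whether two analysts would assemble different comparator groups for the same hypothesis. Aim 3 has some weight: the introduction says that a prospective trial of dronabinol would be justified partly by improvement in mood, craving or negative symptoms without worsening of psychosis or cognition.

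**Working it through.** The plan gives no figure for Aim 3, so the check sets the texts side by side and then follows each reading to its consequence.

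**Step 1. Pre ratings described by the scan-day sentences, for the five groups in (b)**

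| Measure | G2 | G3 | G4 | G7 | G8 |
|---|---|---|---|---|---|
| Mood | yes | yes | yes | yes | yes |
| Negative symptoms | yes | yes | yes | not named | not named |
| EPS | yes | yes | yes | not named | not named |
| Psychotic symptoms | yes | yes | yes | not named | not named |

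With 25 per group (section 4, Overview), the three lower rows have a described Pre value in 3 × 25 = 75 planned participants, against 5 × 25 = 125 in the groups that (b) names.

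**Step 2. Text that points the other way or is open**

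- The lay abstract says the T1 assessments hardly differ between groups.
- The post-scan sentence in section 4, Day of T1, lists symptom and EPS ratings alongside reward responsiveness, which every group performs, and sets no limit by diagnosis.
- Section 4, Day of T2, puts Groups 4 and 8, and Groups 5-7, through the procedures of Groups 1-3. The exceptions it lists for Groups 4 and 8 concern study drug and blood sampling, not symptom ratings.
- Section 10 describes the PANSS and the EPS scales without restricting them to any group.
- The attached schedule of events allocates tasks by group. It is not in the public text, so its absence here is not a gap in the plan.

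The supports for the narrow reading are modest. That section 7b states the Pre/Post timing only for G2 would, taken strictly, also exclude G3 and G4, which the scan-day text does rate. The one-week call is safety follow-up and says little about scan-day measurement. Calling EPS a drug side effect says what it is, not who is rated.

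**Step 3. Consequence of each reading**

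- *G7 and G8 are rated.* All four comparators have change scores and (b) runs as written. Only the scan-day sentence is incomplete.
- *G7 and G8 are not rated.* No change score exists for them on three measures, so they leave those comparisons, and G3 and G4 remain. Who leaves is fixed by diagnosis before any T2 result is seen.

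**Step 4. What stays the same**

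The randomised contrast for dronabinol is G2 versus G3: 25 + 25 = 50 participants under either reading. If it were estimated from a model pooling all groups (an assumption, since the plan names no model for these measures), the between-group residual degrees of freedom would be 125 − 5 = 120 or 75 − 3 = 72, both ample. Mood keeps all five groups. The endpoints in section 7a (reward activation, connectivity and reward responsiveness) use none of these ratings.

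**The case for a change.** The best case for a change is that the mismatch sits in the plan's own words. The three scan-day sentences form a deliberate allocation by diagnosis: mood for everyone, cannabis scales for those with cannabis use disorder, symptoms and EPS for those with schizophrenia. Sending the control groups through the procedures of Groups 1-3 arguably carries those conditions along; read literally the other way, it would require craving ratings from G4 and G8 too. The unrestricted post-scan sentence could supply only a Post value. The scope of (b) is also loose: it covers psychotic symptoms, which (a) expects not to change, and it does not say whether craving, high and liking, which appear in the Aim 3 heading, belong to it. If they do, G4 and G8 lack a described Pre rating on those scales.

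That the wording is untidy stands, and aligning it with the schedule would help a reader. The claim that analysts could diverge does not stand. Where no Pre rating exists, nobody can include the group in a Pre-to-Post comparison; where one exists, the plan already names the group. The same holds for craving, high and liking. Nor is the lost information worth much: G7 and G8 differ from G2 in diagnosis and were not randomised against it, so neither can isolate the effect of dronabinol in these patients as G3 can.

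**Conclusion.** No change to the plan is needed. There is a genuine tension between the comparator list in section 7b and one sentence of the scan-day text, but it is a detail that the schedule of events or the data themselves will settle, and no conclusion depends on how. At its largest it removes two non-randomised groups, 2 × 25 = 50 of the 100 planned comparator participants, from three measures of a secondary aim. The 25 versus 25 randomised comparison, mood and all endpoints in section 7a stay as planned.

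This rests on two assumptions: that the schedule is consistent about who is rated at Pre, and that analysts compute change only where both ratings exist. It would be courteous to ask the sponsor to confirm from the schedule whether G7 and G8 receive pre-scan symptom and EPS ratings, and whether (b) is meant to cover psychotic symptoms. That is an editorial query, not a flaw in the analysis.

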The Dartmouth Department of Psychiatry has a Data Safety Monitoring Board (DSMB) to independently oversee clinical trials and other studies. The DSMB for this study will be composed of at least three people and will include (at minimum) a clinician knowledgeable about schizophrenia and substance use disorders, an investigator familiar with fMRI, and a biostatistician, all of whom will be independent of the study group. The group will follow the NIH policy for data and safety monitoring and guidelines as published on <http://www.miaid.nih.gov/dmid/clinresearch/dsm.htm>. Study data regarding participant enrollment, characteristics, symptoms, substance use, adverse events and serious adverse events will be submitted to the DSMB twice yearly for review and analysis. The DSMB will review study data to oversee the safety of study participants and conduct of the study. It will advise the PI (and the Departmental Research Committee) on continuation of the study and provide reports to the IRB regarding recruitment of appropriate participants and presence of adverse effects.

9. Genetics:

Does any part of the study involve genetic analysis of biological specimens?

Yes No *If yes, respond to **Genetics Attachment C***

10. Instruments:

Describe each instrument, if any, used to collect data in this study.

Attach copies of any questionnaires, surveys, or interview questions. If the research involves interviews that could evolve as the research progresses, include a list of discussion topics and any "starter" questions for each topic that can reasonably be expected to be covered. If a draft of a written questionnaire or survey is attached, it should be clearly labeled as such and a final version should be sent to CPHS for review before data collection begins.

Pre-screening: As part of our recruitment, a short, web-based survey will be used to prescreen people interested in participating in the study. The survey will ask a series of questions targeting the most common and clearly defined criteria for inclusion (e.g., age, willingness to be abstinent during the study, current cannabis use). The screening survey will provide feedback as to whether or not people may be eligible to participate and collect contact data on those appearing eligible. The results of the survey will be for recruitment purposes and not a part of the study data.

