Risks from Cannabis and Dronabinol - Symptom Exacerbation: In this study, the most prominent activity associated with risk is the administration of cannabis and dronabinol, particularly to Groups 1, 2 and 3 who have a diagnosis of SCZ and a co-occurring CUD. Multiple strategies will be used to protect patients with SCZ-CUD who are given cannabis or dronabinol (or double-blinded cannabis and placebo) from relapse of psychosis. First, patients will be under treatment for their psychosis during the study, and must be stable with a low level of symptoms in order to participate. Second, all participants who will be exposed to cannabis or dronabinol during the study will be current active cannabis users who are used to the effect of cannabis. Third, with our pilot work, we have established a safe dose of dronabinol (two 7.5 mg capsules) and of cannabis for the cigarette for these patients, which did not produce untoward effects. We will use these doses in this study. All participants given cannabis or dronabinol (or double-blinded placebo cannabis and dronabinol) will be monitored closely in the laboratory until it is determined by the MD that they are able to be safely discharged. If symptoms develop and do not remit, patients will be offered inpatient treatment, as appropriate. Moreover, for participants given cannabis, dronabinol or placebo, we will attempt to contact them both the day after T2 and one week later to assess their status. If additional check-ins or clinical interventions are needed, it will be coordinated by the study team. In our pilot study with 15 patients in a similar protocol, none had problematic symptoms and no patients required additional medication or inpatient treatment. With the use of the strategies described here, study participation is unlikely to precipitate significant symptom exacerbations, but research staff, who have substantial clinical experience with this population, will be prepared to act immediately to treat patients and maintain safety if an exacerbation does occur.

Risks from Cannabis and Dronabinol - Other: Known effects of dronabinol and cannabis are listed below. These side effects occurred when people took dronabinol regularly. They are also known to occur when people smoke cannabis. We do not know how likely it is that these

side effects will occur if the medication is taken once as it will be in this study. Participants will be monitored frequently in the lab all day on the days they take these drugs.

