a) The reasons why the sponsor or funding agency is not accepting responsibility for research-related injury.

NIH does not cover the cost of injury or illness.

b) Summary of risks as related to potential costs that could be incurred as a result of research-related injury or illness.

It is possible that a participant could have a severe psychiatric reaction to the drugs used in the study or to the scanning or other study procedures. Should this occur, hospitalization could be required. However, we believe this is extremely unlikely given our pilot work establishing a safe dose of cannabis and dronabinol for this study and since all participants who get study drug will be cannabis users, some schizophrenia patients will be taking antipsychotic medication already, and all will be required to be psychiatrically stable as indicated by outpatient treatment for the past month. If a participant needs psychiatric hospitalization, it will be billed to their insurance.

c) Describe reasons for requesting that DHMC or Dartmouth College provide coverage for research-related injury or illness, which is not standard policy.

We are not requesting this.

29. Participant Remuneration:

Will participants be paid for their time, reimbursed for travel or meal expenses, or receive any sort of "gift" for participating in this study?

Yes No

If yes, please describe in detail:

Note: Participant remuneration is not considered a benefit of being in a research study. CPHS will consider the amount of payment in relation to the time needed and any inconvenience to participants. Payment, reimbursement, or gifts should not be in an amount that would be coercive to the participant population.

If study is to be done at the VA, specific questions need to be answered if a participant is being paid "in excess of reimbursement for travel." Please contact the CPHS office if you need more information.

Participants with schizophrenia will receive a \$25 gift card for attending the informational session to learn about the study.

All participants in Groups 1-4 (SCZ-CUD and SCZ only) will be paid:

- \$25 for completing the Screening Visit paid as a gift card on the day of the visit
- \$50 for the Neuropsych Baseline Visit paid as a check at the end of the study
- \$100 for T1 Scan day paid as a check at the end of the study

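### Section 8 sends serious adverse events to the DSMB twice yearly with the routine data, and the plan states no faster route and no event that prompts review between reports

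*Combined protocol and SAP*

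**What the plan says.** Section 8 (Data and Safety Monitoring) describes an independent board of at least three people. It includes a clinician who knows schizophrenia and substance use disorders, an fMRI investigator and a biostatistician. Its data flow is a single list, ending with the statement that "adverse events and serious adverse events will be submitted to the DSMB twice yearly for review and analysis". On its function, the section says "It will advise the PI (and the Departmental Research Committee) on continuation of the study", and that it reports to the IRB; neither carries a timetable. The section also says "The group will follow the NIH policy for data and safety monitoring", with published guidelines, without giving their content.

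Section 14 states that "the most prominent activity associated with risk is the administration of cannabis and dronabinol", particularly for Groups 1 to 3. On the pilot of 15 patients it reports that "none had problematic symptoms and no patients required additional medication or inpatient treatment". Section 28 says "It is possible that a participant could have a severe psychiatric reaction to the drugs used in the study" and "Should this occur, hospitalization could be required", while adding that "we believe this is extremely unlikely".

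Care of the individual is described in detail. Under Section 4 (Day of T2), a physician clears each patient in Groups 1 to 3 before dosing, a doctor clears discharge, rescue drugs are at hand, and unstable participants are observed or admitted. Contacts follow the next day, at about one week and at about 30 days. Section 10 has adverse events reviewed at every visit.

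**The concern.** The DSMB is the independent body with a say on whether dosing goes on. The only schedule stated for giving it serious adverse events is the routine half-yearly one. The event at issue is the one the protocol itself ranks as its leading risk: a psychiatric reaction to THC in a patient with schizophrenia, serious enough for admission.

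Since each person is dosed once, independent review of such an event can only protect those dosed later. Its speed therefore matters across participants, even though it does nothing for the person already affected. On the stated schedule, an admission shortly after one report could go unseen by the board until the next, while dosing continues.

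**Working it through.** **Text check.** Places where a faster route or a trigger might be stated:

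- Section 8: twice-yearly submission; no ad hoc meeting, threshold or trigger.
- Section 14, overall approach to protection: the investigator and the DSMB monitor safety during the study; no route or timing.
- Section 4 (Day of T2), Section 10 (Safety Assessment), the remainder of Section 14, and Section 18: clinical cover, follow-up and event tracking for individuals; nothing sent onward to the DSMB.
- Section 28: admission is foreseen; no reporting step.
- Section 30: an IND number is given; no safety reporting procedure.

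**Scale.** The plan gives no event rate, so there is no figure of its own to reproduce. Inputs from the plan are 25 per group, Groups 1 and 2 on active drug (2 × 25 = 50 patients), 5 years of enrollment (Section 13) and two reports a year (Section 8). Assumptions are even accrual and a range of event rates p, where an event is a serious adverse event, or an admission for a reaction, after T2 dosing.

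- Active-drug patients with schizophrenia and cannabis use disorder per half-year: 50 / 10 = 5.
- Longest wait: about 6 months. An event at a random point in the interval waits 3 months on average, in which 3 × 50/60 = 2.5 more are dosed.
- Under a 7-day deadline: 50 × 7 / (5 × 365) = 0.19 more are dosed before the DSMB is told.

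The first event tends to fall earlier in an interval as the rate rises, so the wait was also simulated: 200,000 runs per rate, 50 dosings uniform over 60 months, a report every 6 months.

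| Assumed rate p | At least one event per half-year, 1 − (1 − p)^5 | Mean wait from first event to next report (months) | Mean further active-drug patients dosed | Expected further events among them (p × previous column) | Likelihood of 0 of 15, (1 − p)^15 |
|---|---|---|---|---|---|
| 1% | 4.9% | 3.0 | 2.5 | 0.025 | 0.86 |
| 5% | 22.6% | 3.1 | 2.6 | 0.13 | 0.46 |
| 10% | 41.0% | 3.3 | 2.7 | 0.27 | 0.21 |
| 18% | 62.9% | 3.4 | 2.9 | 0.5 | 0.05 |

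The 95th percentile of further patients dosed is 6 to 7. At 1%, the chance of no event in all 50 is 0.99^50 = 0.61.

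**What the pilot supports.** The one-sided 95% upper bound from 0 of 15 is 1 − 0.05^(1/15) = 0.181, so rates up to 18% are not excluded. The likelihoods still favour 1% over 10% by about 4 to 1 (0.86 / 0.21). The pilot also pooled cannabis with dronabinol and compared 5, 10 and 15 mg pills, so 18% is not a bound for either study regimen.

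**The case against.** The strongest reply is that Section 8 does not say serious events go to the board only twice a year. It binds the board to NIH policy and published guidelines, and Section 30 places the study under an IND. Either may carry a prompt reporting duty. The text at hand also lacks a portion between Sections 16 and 17. A reader might infer that no faster route exists; the documents do not support that. What stands is narrower: the plan states a half-yearly schedule, and no visible text supplies another route to the DSMB.

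A second reply is that those who can act know at once. Physicians clear patients before dosing and at discharge, psychiatrists are on call, and the investigator monitors throughout. This is right. A reader might infer that participants are left unprotected, and the safeguards in Sections 4 and 14 contradict that. They treat the person already dosed, however, and do not inform the independent body that advises on dosing the next.

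A third reply is that the count of further patients dosed is not a count of harm. This also stands. The expected further events are 0.025 to 0.5 given a first event, and avoiding them would require a pause after that event, which neither the plan nor the proposed change mandates. A reader might also treat 1% and 10% as equally consistent with the pilot because both lie below 18%; the likelihoods show they are not.

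**Conclusion.** The point holds as a cheap improvement. The plan puts serious adverse events on the half-yearly DSMB schedule and states no faster route and no trigger for interim review. Followed as written, it allows a delay of up to about 6 months before the board hears of a serious reaction after dosing. With even accrual of 50 active-drug patients over 5 years, about 2.5 to 3 more would be dosed on average in that wait, against about 0.2 under a 7-day rule.

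That comparison measures how fast the board is told, not harm prevented. The safety effect is modest, and its size depends on an event rate that the documents do not give and that the pilot suggests is low. The conclusion is limited to the text available and would change if the NIH policy or the IND sets a deadline for notifying the DSMB.

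**What to change.** Keep the twice-yearly reports and add to Section 8:

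> Any serious adverse event, or any overnight or inpatient admission for a reaction, occurring after T2 dosing in Groups 1-3 or 5-7 will be sent to the DSMB within 7 days of the study team learning of it, identified by coded arm, and the DSMB will advise whether T2 dosing in that diagnosis group continues or pauses.

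If the NIH policy or the IND already sets a deadline for reporting to the DSMB, state that deadline instead. The 7 days is a proposal that the sponsor can adjust, and any numerical pause rule is best left to the board.

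The change adds a sentence or two and needs no new committee or staff. Expected notices from the 50 active-drug patients are 50 × p = 0.5, 2.5, 5 and 9 over 5 years at 1%, 5%, 10% and 18%. If all 150 dosed participants shared the rate, the totals would be 150 × p = 1.5, 7.5, 15 and 27. The downside is occasional ad hoc contact with the board and a possible short pause in dosing.
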